2. LIST OF ABBREVIATIONS

Term	Definition / description
ACE	Angiotensin Converting Enzyme
AE	Adverse event
AESI	Adverse event of special interest
ALT	Alanine transaminase
ANCOVA	Analysis of covariance
ARB	Angiotensin Receptor Blocker
ARNI	Angiotensin Receptor blocker-Neprilysin Inhibitor
ASA	Acetylsalicylic acid
AST	Aspartate transaminase
ATC	Anatomical-Therapeutic-Chemical
AUC	Area under the curve
BI	Boehringer Ingelheim
BIcMQ	Boehringer Ingelheim customized MedDRA Query
BMI	Body mass index
BP	Blood pressure
bpm	beats per minute
CEC	Clinical Event Committee
CIF	Cumulative Incidence Function
CKD-EPI	Chronic Kidney Disease Epidemiology Collaboration
CRT	Cardiac resynchronisation therapy
CTP	Clinical Trial Protocol
CTR	Clinical Trial Report
CV	Cardiovascular
DAOH	Days alive and out of hospital
DBL	Data base lock
DBP	Diastolic Blood Pressure
DKA	Diabetic ketoacidosis
DM	Diabetes mellitus
ECG	Electrocardiogram
eCRF	Electronic Case Report Form
EF	Ejection Fraction

Term	Definition / description
eGFR	Estimated glomerular filtration rate
EMA	European Medicines Agency
EoT	End-Of-Text
EOT	End of treatment
EudraCT	European Clinical Trials Database
GI	Gastrointestinal
HbA _{1c}	Glycosylated haemoglobin
HF	Heart failure
HFE	Heart failure event
HLT	High level term
HR	Hazard ratio
IC	Informed consent
ICD	Implantable Cardioverter Defibrillator
ICH	International Conference on Harmonisation
iPD	Important protocol deviation
IRT	Interactive Response Technology
ITT	Intention-to-treat
KCCQ	Kansas City Cardiomyopathy Questionnaire
KCCQ-TSS	Kansas City Cardiomyopathy Questionnaire Total Symptom Score
kg	kilogram
LLT	Low level term
LVEF	Left ventricular ejection fraction
MAR	Missing at random
Max	Maximum
MCMC	Markov Chain Monte Carlo
MedDRA	Medical Dictionary for Regulatory Activities
mg	milligram
mg/dL	Milligram per decilitre
MI	Myocardial infarction
Min	Minimum
MMRM	Mixed models repeated measures
MNAR	Missing not at random

Term	Definition / description
MRA	Mineralocorticoid Receptor Antagonist
NT-proBNP	N-terminal pro B-type natriuretic peptide
NYHA	New York Heart Association Classification
OC-AD	Observed Case including data After Discontinuation
OC-OT	Observed Case On Treatment
PPS	Per Protocol Set
PT	Preferred term
Q1	Lower quartile
Q3	Upper quartile
RS	Randomised set
SAE	Serious adverse event
SAS	Statistical Analysis System
SBP	Systolic blood pressure
SCR	Screened set
SD	Standard deviation
SE	Standard error
SGLT-1	Sodium-glucose co-transporter 1
SGLT-2	Sodium-glucose co-transporter 2
SI	Système international d'unités
SLR	Sequential linear regression
SMQ	Standardized MedDRA query
SOC	System organ class
TBILI	Total bilirubin
TS	Treated set
TSAP	Trial statistical analysis plan
ULN	Upper limit of normal
UTI	Urinary tract infection

3. INTRODUCTION

As per the International Conference on Harmonisation (ICH) E9 guidance ([1](#)), the purpose of this document is to provide a more technical and detailed elaboration of the principal features of the analysis described in the protocol, and to include detailed procedures for executing the statistical analysis of the primary and secondary variables and other data.

This Trial Statistical Analysis Plan (TSAP) assumes familiarity with the Clinical Trial Protocol (CTP), including Protocol Amendments. In particular, the TSAP is based on the planned analysis specification as written in CTP Section 7 “Statistical Methods and Determination of Sample Size”. Therefore, TSAP readers may consult the CTP for more background information on the study, e.g., on study objectives, study design and population, treatments, definition of measurements and variables, planning of sample size, randomisation.

SAS® Version 9.4 or later will be used for all analyses.

4. CHANGES IN THE PLANNED ANALYSIS OF THE STUDY

In the CTP, a stratified win ratio is described, but the weighting method for each stratum is not mentioned. Therefore, the weighting method to be used has been described here in [Section 7.4.1](#).

In the logistic regression models used for the binary endpoint variables (e.g. improvement in KCCQ-TSS of ≥ 10 points after 90 days of treatment), an additional continuous covariate (baseline KCCQ-TSS score) is included (see [Section 7.5.2](#)).

5. ENDPOINTS

5.1 PRIMARY ENDPOINT

The primary endpoint is specified in the CTP Section 2.1.2.

An HFE is:

- A hospitalization/ER visit OR
- An urgent care visit OR
- An Outpatient visit

With all of the following:

- The question “Was visit related to the primary diagnosis or worsening of heart failure in the opinion of the treating physician?” is answered yes
- At least one symptom of
 - o dyspnea,
 - o decreased exercise tolerance,
 - o fatigue,
 - o edema
 - o other symptoms of worsened end-organ perfusion or volume overload
- At least two physical examination findings OR (one physical examination finding and at least one laboratory criterion).
 - o Physical examination are
 - peripheral edema,
 - increased abdominal distention or ascites,
 - pulmonary rates/crackles/crepitations,
 - Increased jugular venous pressure and/or hepatojugular reflux,
 - S3 gallop,
 - Clinically significant or rapid weight gain thought to be related to fluid distention,
 - other
 - o Laboratory criteria are:
 - Increased BNP or NT-proBNP,
 - radiological *or* ultrasonographic evidence of pulmonary congestions,

- non-invasive diagnostic evidence of clinically significant elevated ventr. filling pressure or low cardiac output
- invasive diagnostic evidence with right heart catheterization showing a pulmonary capillary wedge pressure ≥ 18 mmHg, central venous pressure ≥ 12 mmHg or cardiac index < 2.2 L/min/m²
- Other
- Intensification of therapy (significant augmentation of oral diuretics, IV diuretics', vasoactive agent, or mechanical or surgical intervention)

5.2 SECONDARY ENDPOINTS

5.2.1 Key secondary endpoint

Not applicable.

5.2.2 Secondary endpoints

[figure not shown]
Secondary endpoints are specified in the CTP Section 2.1.3. Regarding the CV death endpoint, adverse events on the eCRF death event form where the primary cause of death is CV death or unknown cause of death, will be classed as CV death.

Regarding the secondary endpoint “occurrence of HHF until 30 days after initial hospital discharge”, HHFs are defined as the subset of HFEs where the investigator has checked the hospitalisation tick box.

Regarding the secondary endpoint “occurrence of chronic dialysis or renal transplant or sustained reduction of $\geq 40\%$ eGFR Chronic Kidney Disease Epidemiology Collaboration Equation ((CKD-EPI)cr), or

- sustained eGFR (CKD-EPI)cr < 15 mL/min/1.73 m² for patients with baseline eGFR ≥ 30 mL/min/1.73 m²
- sustained eGFR (CKD-EPI)cr < 10 mL/min/1.73 m² for patients with baseline eGFR < 30 mL/min/1.73 m²,

the following applies: an eGFR (CKD-EPI)cr reduction is considered sustained, if it is determined by two or more consecutive post-baseline central laboratory measurements separated by at least 30 days (first to last of the consecutive eGFR values). Chronic dialysis is regarded as chronic if the frequency of dialysis is twice or more per week for at least 90 days. Chronic dialysis and renal transplant will be confirmed by medical review of data from the concomitant non-drug therapy eCRF page.

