## FLOW CHART

Trial Periods	Screen	Randomised Treatment						Follow-up	
Visit	1	2 (in hospital)			3	4	5 (EoT)	Early Discontinuation Visit 	6 (FUP) (Phone Call)
		a	b 	c 					
Days	-4 to 1	1 	3	5	15	30	90		EoT + 7 days
Time window for visits (days)		None	±1	±1	±3	±3	±7		+ 7
Informed consent 	X								
Demographics	X								
Medical history	X								
Physical examination	X						X	X	
Review of in-/exclusion criteria 	X	X							
Randomisation (IRT)		X							
Weight		X			X	X	X	X	
Height		X							
Vital signs 		X	X	X	X	X	X	X	
Safety lab: blood tests 		X	X	X	X	X	X	X	
Safety lab: urinalysis including ketones 		X			X	X	X	X	
Urine Pregnancy test 	X						X 	X	
HbA1c 		X					X	X	
eGFR (CKD-EPI)cr formula 		X	X	X	X	X	X	X	
NT-proBNP (central lab) 		X	X	X	X	X	X	X	
12 lead-ECG 		X					X 	X	
KCCQ		X			X	X	X	X	
Patient Global Impression of Severity of HF Symptoms		X			X	X	X	X	
Clinical Congestion Score		X	X	X	X		X	X	
NYHA Classification		X			X	X	X	X	
HCRU		X			X	X	X	X	
All AEs/SAEs/AESIs 	X	X	X	X	X	X	X	X	X
Concomitant therapy		X	X	X	X	X	X	X	
Dispense trial medication		X				X			
Compliance check					X	X	X	X	
Return medication						X	X	X	
Completion of patient participation (End of Study (EOS))							(X) 		X

 Day of Randomisation / Day of first intake of randomised medication. All Visit 2a assessments must be performed before the first dose is taken in hospital. Assessments from Visit 2a will be used as baseline values.

 Visit 2b and 2c will only be performed, if the patient is still in hospital.

Proprietary confidential information © 2020 Boehringer Ingelheim International GmbH or one or more of its affiliated companies

- 3 Patients who discontinue trial treatment prematurely should undergo the Early Discontinuation Visit as soon as possible and the Follow-up (FUP) Visit 7 days thereafter. Patients should be followed up until Visit 5 (day 90) according to their planned visit schedule.
- 4 Written informed consent must be obtained before any other assessment is performed.
- 5 Blood pressure and heart rate will be measured with the patient seated and rested for at least 5 minutes. Vital signs at Visit 2a need to be checked before first trial medication intake.

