### 3. DESCRIPTION OF DESIGN AND TRIAL POPULATION

#### 3.1 OVERALL TRIAL DESIGN

This is a randomised, double-blind, parallel-group, placebo controlled, multinational and multicentre study.

A total of approximately 500 male and female patients admitted to the hospital for acute HF will (de novo or decompensated chronic HF) be randomised (1:1) in the study in about 13 countries.

The pre-screening period will start when patients are admitted. Screening (Visit 1) and randomisation (Visit 2a) can happen on the same day. Randomisation should occur after at least 24 hours and no later than 5 days after admission and before discharge when patients fulfil criteria to indicate clinical stability including a stable dose of diuretics. Visit 2 consists of two further visits (Visit 2b and 2c) that will be performed only if the patient is still in hospital. All patients will be treated on top of standard of care. Patients will receive the study drug for 90 days. A follow-up phone call will be performed 7 days after the End of Treatment Visit.

\*Visit 2b and 2c are optional and will only be performed if the patient is still in hospital

\*\* Visit 6 will be performed as a phone visit

Figure 3.1: 1 Trial design

The primary endpoint will be assessed at Visit 5.

Patients who prematurely stop medication should have an End of Treatment Visit but be followed up until their planned Visit 5 (Day 90) according to the visit schedule.

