 Please note: Troponin elevations are frequently seen in patients with acute heart failure and therefore are not sufficient for a diagnosis of AMI. In order to exclude an AMI, concomitant objective evidence of AMI based on typical symptoms, ECG, and/or cardiac imaging and/or coronary angiography should be available.

Proprietary confidential information © 2020 Boehringer Ingelheim International GmbH or one or more of its affiliated companies

circulatory support, or patients on mechanical ventilation, or patients with planned inotropic support in an out-patient setting.

9. Haemodynamically significant (severe) uncorrected primary cardiac valvular disease planned for surgery or intervention during the course of the study (note: secondary mitral regurgitation or tricuspid regurgitation due to dilated cardiomyopathy is not excluded unless planned for surgery or intervention during the course of the study).
10. Cardiomyopathy due to infiltrative diseases (e.g. amyloidosis), accumulation diseases (e.g. haemochromatosis, Fabry disease), muscular dystrophies, cardiomyopathy with reversible causes (e.g. stress cardiomyopathy), hypertrophic obstructive cardiomyopathy, complex (according to investigator's judgement) congenital heart disease, or known pericardial constriction.
11. Heart failure caused by peripartum cardiomyopathy or Tako-Tsubo cardiomyopathy diagnosed within the past 6 months, or active myocarditis, or uncorrected thyroid disease, or other acute structural heart disease as cause for acute cardiac decompensation (e.g. acute mitral cord rupture as cause for hospital admission for heart failure).
12. Symptomatic bradycardia or third degree heart block without a pacemaker.
13. SBP  $\geq$  180 mmHg at randomisation (confirmed with second measurement after 5 minutes).
14. Atrial fibrillation or atrial flutter with a documented resting heart rate  $>$  110 bpm in ECG performed before randomisation (Visit 2a).
15. Impaired renal function, defined as eGFR  $<$  20 mL/min/1.73 m^2 as measured during hospitalisation (latest local lab measurement before randomisation) or requiring dialysis.
16. Type 1 Diabetes Mellitus (T1DM).

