If this leads to contradictions for the start or end date of a concomitant therapy (e.g. imputed end date before documented start date), a partial end date will be imputed as the end of the interval or a partial start date will be imputed as the start of the interval in the database to resolve this contradiction.

If it is unclear from the partial date, whether a therapy was before or after date of baseline, then it will be assumed, that the therapy started after baseline (similar to worst case rules applied for adverse events).

All other cases or conflicting cases resulting from these imputation rules need to be assessed by the trial team on an individual patient basis.

Missing measurement to confirm “sustained” decrease

An eGFR (Chronic Kidney Disease Epidemiology Collaboration (CKD-EPI)cr) reduction is

considered sustained, if it is determined by two or more consecutive post-baseline central laboratory measurements separated by at least 30 days (first to last of the consecutive eGFR values). If there is no additional measurement ≥ 30 days after the eGFR reduction is observed and the patient dies within 60 days of this measurement, then the eGFR reduction is also considered sustained.

Hospital discharge date

Missing hospital discharge dates will be replaced with the date of the last follow-up.

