6.8 CALCULATION OF TIME TO EVENT

This section describes the calculation of the time to event and the time that patients without an event are in the study (under risk).

Consistent with that approach, the respective time intervals determine the start and end for the derivation of occurrence of a specific event.

For those patients with an event, the time to event is calculated as:

<date of event> - < start date> + 1

For those patients without an event, the time at risk is calculated as:

<date of censoring> - < start date > + 1

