6.8.3 Censoring

The underlying principle is that the censoring date should be the last date a patient was known to be free of an endpoint event (e.g. free of each component of CV death and HFE).

For all endpoints except all-cause mortality and cause-specific death, patients without occurrence of a specific endpoint (composite endpoint or individual components) will be considered censored at the individual day of end-of-study.

The individual day of trial completion will be the latest of:

- last onset of an AE or date of death
- onset dates of adjudicated events
- end of treatment
- last visit date (NYHA class, KCCQ, pregnancy test, vital signs, ECG, or central laboratory)

Censoring is considered independent from study drug intake.

All-cause mortality

A patient without the event will be censored at the latest of:

- individual day of trial completion (without the restrictions defined above for patients with withdrawn consent or lost to follow-up)
- last date known alive from the vital status page

Endpoints of any cause-specific death, e.g. CV death

The same censoring rule as for all-cause mortality applies, and in addition, date of death if died from other causes than the one specified in the endpoint.

Endpoints based on laboratory data only

Patients who already fulfil the respective condition at baseline are not considered in the number of patients at risk for this endpoint.

If a baseline laboratory measurement is not available for the parameter of interest, it is assumed that the patient did not experience the condition corresponding to the endpoint at baseline and the patient is included in the patients at risk for this endpoint. Patients without an event and available post-baseline laboratory measurement will be considered censored at the date of last laboratory sampling of the corresponding parameter. Patients with a missing baseline laboratory value required to derive a change from baseline and patients without laboratory data following the baseline measurement will be censored on the date of randomisation.

Composite endpoints (analysed using a time-to-event approach)

Only patients that are included in the analyses for all components of the composite endpoint will be included in the analysis of the composite.

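### The 90-day dialysis criterion in the renal composite is as long as the treatment period, so its dialysis limb can register almost nothing within follow-up, and SAP 6.6.2 has no rule for dialysis cut short by death or last contact

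*SAP*

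**What the plan says.** The composite (Protocol 2.1.3, SAP 5.2.2) combines chronic dialysis, renal transplant, a sustained eGFR reduction of 40% or more, and sustained eGFR below a threshold that depends on baseline.

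- **Dialysis criterion, SAP 5.2.2:** "Chronic dialysis is regarded as chronic if the frequency of dialysis is twice or more per week for at least 90 days". Chronic dialysis and transplant "will be confirmed by medical review of data from the concomitant non-drug therapy eCRF page".
- **Entry, Protocol 3.3.3, criterion 15:** excludes patients on an eGFR limit ("latest local lab measurement before randomisation) or requiring dialysis"), so any dialysis that counts must begin on study.
- **Treatment length, Protocol 3.1:** "Patients will receive the study drug for 90 days".
- **Follow-up:** the Flow Chart puts Visit 5 at Day 90 ± 7 and a phone call 7 to 14 days after end of treatment. For patients who stop drug early it says "Patients should be followed up until Visit 5 (day 90) according to their planned visit schedule", and Protocol 6.2.3 makes Visit 5 the end of study for them. Concomitant therapy is marked up to Visit 5 and at the Early Discontinuation Visit, but not at the call.
- **eGFR, SAP 5.2.2 and 6.6.2:** a reduction must be confirmed by central laboratory values at least 30 days apart. If no such later value exists and "the patient dies within 60 days of this measurement, then the eGFR reduction is also considered sustained".
- **Dialysis in SAP 6.6.2:** the only rules that touch it are those for incomplete or conflicting therapy dates.

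**The concern.** A duration requirement is a natural part of an endpoint called chronic dialysis, because it keeps out short acute episodes. The difficulty is that the required duration equals the planned treatment period, while dialysis cannot already be in progress at entry. Almost any dialysis that starts on study is therefore still short of the criterion when its scheduled recording stops.

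The SAP recognises the same problem for eGFR, where death can prevent confirmation, and supplies a rule. It supplies none for dialysis interrupted by death or by the end of follow-up.

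What is at stake is interpretation. Protocol 3.2 names renal function as a focus of the safety assessment. A table with no dialysis events could be taken as reassurance when it mostly reflects the length of follow-up.

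**Working it through.** The plan gives no figure of its own to reproduce. The check is day arithmetic.

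**Inputs.** Required duration 90 days (SAP 5.2.2). Day 1 is the day of randomisation and first dose; Visit 5 falls on Day 83 to 97; the call comes 7 to 14 days after end of treatment (Flow Chart, Protocol 6.2.3).

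**Formula.** Counting both the start day and the last observed day L, the latest start that reaches 90 observed days is L − 90 + 1 = L − 89.

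| Last observation | L | Latest qualifying start | Share of start days 1–90 |
|---|---|---|---|
| Visit 5, earliest | 83 | 83 − 89 = −6, none | 0% |
| Visit 5, nominal | 90 | 90 − 89 = Day 1 | 1/90 = 1.1% |
| Visit 5, latest | 97 | 97 − 89 = Day 8 | 8/90 = 8.9% |
| Call, nominal (90 + 7) | 97 | Day 8 | 8.9% |
| Call, late in its window (90 + 14) | 104 | 104 − 89 = Day 15 | 15/90 = 16.7% |
| Call, extreme of all windows (97 + 14) | 111 | 111 − 89 = Day 22 | 22/90 = 24.4% |

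If the start day is not counted, each latest start moves one day earlier. The call rows are generous, because the Flow Chart does not schedule concomitant therapy there.

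**Can the eGFR limb catch the same patients?** After Day 5, eGFR is scheduled at Days 15, 30 and 90.

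- Fall seen by the Day 30 visit: Visit 5 can confirm it, 90 − 30 = 60 days later. With visit windows the gap is 83 − 33 = 50 to 97 − 27 = 70 days, always above 30.
- Fall first seen after Day 30 in a patient still on drug: the only scheduled value left is Visit 5, so it normally cannot be laboratory-confirmed.
- Fall first seen at an Early Discontinuation Visit, which includes eGFR: Visit 5 can confirm it if that visit falls by Day 90 − 30 = 60 (Day 53 to 67 across the Visit 5 window).
- Death within 60 days of an unconfirmed fall: counted under SAP 6.6.2.

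The two limbs overlap, but not fully. A patient still on drug who starts dialysis after the Day 30 visit, without an earlier qualifying eGFR, is generally missed by both unless the death rule applies.

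**Size.** These are limits of observation. The documents give no expected dialysis rate, so no count of missed events can be derived.

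**The case against.** **No sentence says that ongoing dialysis is scored as no event.** Dialysis goes to medical review, and unresolved therapy dates go to the trial team case by case. This is fair as far as it goes: the SAP does not say how duration is judged when there is no end date. But the review is described as confirming chronic dialysis, the date rules deal with incomplete or conflicting dates, and neither waives the 90 days. If reviewers are meant to count ongoing dialysis, the SAP should say so.

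**A reader might infer that these patients have no event in the composite.** The documents do not support that. Only the dialysis limb is affected; transplant and the eGFR routes above remain open.

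**A reader might infer that SAP 6.8 formally closes the window at Visit 5.** Section 6.8 says that "the respective time intervals determine the start and end for the derivation of occurrence of a specific event", and the end-of-study day in 6.8.3 depends partly on the "last visit date (NYHA class, KCCQ, pregnancy test, vital signs, ECG, or central laboratory"), none of which the Flow Chart schedules at the call. But SAP 6.8.2 dates composite events by the earliest component onset, and sustained laboratory events by the first qualifying measurement. The interval may therefore govern only when an event begins. The limit rests mainly on where and until when dialysis is recorded.

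**Serious adverse events are followed beyond the trial (Protocol 5.2.7.2.2).** True, but SAP 5.2.2 does not name them as a source for dialysis.

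**The stakes are low.** This stands. Secondary endpoints are exploratory (Protocol 7.1, SAP 7.5.2). SAP 7.8.1.3 tabulates acute renal failure events and creatinine at least twice baseline and above the upper limit of normal, and SAP 7.8.2 plans eGFR models over time and CKD-stage shifts, all without a 90-day condition.

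**Conclusion.** The point holds as a minor one. With a 90-day criterion, 90 days of treatment and no dialysis at entry, the dialysis limb can register only starts by Day 1 to Day 8 within the scheduled record, and by Day 22 at the outer limit. There is no rule for dialysis ongoing at death or last contact, although unconfirmed eGFR reductions have one for death.

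This assumes that the 90 days must be observed and that the eCRF therapy page is the source, as SAP 5.2.2 is written. The protocol footnote to the word sustained and the further-endpoint sections are not in the text available, so a related renal analysis may already be planned there.

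Two further inferences should be resisted. The planned death rate in Protocol 7.5 does not size the gap, because it covers deaths from any cause and says nothing about dialysis. Nor is the eGFR confirmation rule at fault: requiring confirmation is reasonable given the initial eGFR decrease on empagliflozin described in Protocol 1.4.2.

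**What to change.** The change is to the analysis only.

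1. Keep the composite as defined as the main version.
2. Add to SAP 6.6.2, with an entry in SAP Section 4, one supplementary version that also counts dialysis meeting the SAP's weekly frequency criterion and still ongoing at last contact or at death. Flag each such case with its observed duration in days.
3. State with the result that the 90-day dialysis limb is largely unobservable within follow-up, so that few or no dialysis events are not read as evidence of absence.

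**Cost.** One paragraph, one Section 4 entry, one sentence and one supplementary table, using data already collected.

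**Downside.** The supplementary version may admit some acute or transient dialysis, for example dialysis begun shortly before death, and possibly unequally between arms. The duration flag makes such cases visible, and the main version is unchanged.
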